-----------------------------------	--

Exclusion Criteria (continued)	
7. To avoid drug-drug interactions, subjects requiring the following will be excluded:
 
 
• tricyclic antidepressants, which may reduce the efficacy of imidazoline derivatives; and
 
• beta-receptor blockers, to avoid the risk of excessive bradycardia.
 

N	
Total enrollment will depend on subject drop-out rates. Approximately 250 to 500 subjects: enrollment will continue until a minimum total of 300 subjects (across this protocol and earlier lofexidine clinical studies expected to meet FDA safety database requirements) have been treated with clinically relevant doses of lofexidine for a minimum of 7 days. A target of at least 50 subjects each treated for clinical scenarios involving methadone or buprenorphine treatment will be enrolled (i.e., a total of 50 subjects receiving full or partial dose reduction from methadone, methadone-assisted withdrawal, and other methadone treatment scenarios and a total of 50 subjects receiving full or partial dose reduction from buprenorphine, transition to buprenorphine maintenance, and other buprenorphine treatment scenarios).

Safety Endpoints	
 
• Occurrence, seriousness, severity, and causality assessment of adverse events (AEs).
 
• Occurrence of AEs of special interest (i.e., orthostatic hypotension, orthostatic bradycardia, syncope).
 
• Occurrence of AEs not related to opioid withdrawal.
 
• Descriptive evaluation of vital signs (actual and change from baseline) for each time point.
 
• Descriptive evaluation of the three C-SSRS subscales (suicidal ideation, suicidal behavior, and intensity of suicidal ideation).
 
• Shifts from baseline in physical examination findings.
 
• Descriptive evaluation of clinical laboratory tests of hematology, chemistry, and urinalysis (actual and change from baseline).
 
• Descriptive evaluation of ECG (actual and change from baseline).
 

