### 11.2.2 Exclusion Criteria

Subjects who meet any of the following criteria will not be allowed to participate:

1. Be a female subject who is pregnant or lactating.
2. Have a very serious medical illness not under control as detailed below.
  - Serious medical illness will be determined at Screening by:
    - medical history;
    - physical examination;
    - 12-lead electrocardiogram (duplicate);

- clinical laboratory tests, including standard lab tests, an infectious disease panel for syphilis (subject is excluded if positive for active syphilis as per required laboratory tests; see also Section 15.5.4.2) and hepatitis (positive results do not exclude a prospective subject from participation unless there is an indication of active liver disease); and
- tuberculin test (purified protein derivative [PPD]) and/or a chest x-ray (a positive PPD result does not exclude a prospective subject from participation, but if diagnostic tests [e.g., chest x-ray] indicate that active disease is present, the subject will be excluded from participation; see also Section 15.5.4.2).
- Have active self-reported acquired immune deficiency syndrome (AIDS) or self-reported human immunodeficiency virus (HIV) positive status and taking retroviral medications currently or within the past 4 weeks.
- Have an unstable psychiatric condition (e.g., suicide risk, per Investigator judgment).

3. Current dependence (based on the M.I.N.I.) on any psychoactive substance (excluding caffeine, nicotine, and the subject's current opioid-dependence agent, which can include methadone and buprenorphine, for example, in agonist-maintained subjects) that requires detoxification or dose reduction as part of the pre-defined individual subject withdrawal treatment goal.
4. Have participated in an investigational drug study within the past 30 days.
5. Have history of lofexidine exposure in a prior clinical trial or otherwise.
6. Abnormal cardiovascular exam at screening, including any of the following:
  - clinically significant abnormal electrocardiogram (ECG) (e.g., second or third degree heart block, uncontrolled arrhythmia, or QTcF intervals greater than 450 msec for males and greater than 470 msec for females);
  - resting pulse less than 55 bpm or symptomatic bradycardia;
  - resting systolic blood pressure less than 95 mmHg or symptomatic hypotension;
  - resting diastolic blood pressure less than 65 mmHg;
  - resting blood pressure greater than 155/95 mmHg; or

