## 15.1 Screening Assessments

Subjects seeking treatment for opioid dependence at one of the study sites will be screened for study enrollment. Screening assessments must be completed within a 9-day time period. The screening visit will have a visit window of  $\pm 2$  days. Subjects will not be out of compliance if visit windows extend because of extraordinary events that make it impossible for subjects to complete a screening within the  $\pm 2$ -day window (e.g., holidays, vacations, personal emergencies). Determination of the maximum visit window deviation is, however, at the discretion of the medical monitor. Written informed consent must be obtained from all study subjects before initiation of any study procedures.

The following screening assessments must be completed during screening after determining eligibility and written informed consent is obtained: height; weight; vital signs (sitting/standing blood pressure and pulse; respiration; and temperature); blood collection for standard clinical safety laboratory assessments (including hematology and biochemistry); urine sample for confirmatory drug testing, urinalysis, and pregnancy assessment (if female); and infectious disease assessment (see Section 15.5.4.2) and a chest x-ray if a past PPD skin test for tuberculosis was positive.

The urine sample collected will be divided into two aliquots: one sample will go to the central lab for urinalysis; the other sample will be used for “dipstick” analysis of pregnancy and qualitative drug screening.

The assessments listed below must also be performed during screening.

- 12-lead ECGs (in duplicate) will be done on one day during the screening period at 8 AM (or as close to 8 AM as possible) and at 11:30 AM. Note that a time delay for the 8 AM ECG will not be considered a protocol deviation, but that the second ECG should be taken 3.5 hours after the first ECG.
- Medical and smoking/alcohol history.
- Complete physical examination.
- Mini International Neuropsychiatric Interview (M.I.N.I.) [18, 19]. The M.I.N.I. will be performed once at screening only to (1) establish that each potential subject is opioid-dependent (inclusion criterion #2) and (2) determine the absence of major psychiatric disorders (exclusion criterion #3).
- Prior medications will be recorded to capture all medications taken in the past 30 days.
- All opioids of abuse the subject has used will be recorded.

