## 15.2 Baseline Assessments

The Baseline period is the morning of admission to the study, before dosing. Prospective subjects who meet all eligibility criteria must be admitted to the study in time to give the first dose of study medication at 8 AM ( $\pm 30$  minutes).

The assessments listed below will be performed during the Baseline period before dosing.

- SOWS-Gossop.
- COWS.
- Vital signs (resting [sitting or recumbent, if applicable]) and standing blood pressure and pulse; respiration, temperature) measurements.
- Repeat pregnancy assessment (by “dipstick”), if female.
- Repeat urine drug screen (by “dipstick”).
- Update Inclusion/Exclusion Criteria form to reflect Baseline assessments.
- Update prior medication form to capture any new medications since screening.
- Update complete physical exam form to capture any new physical findings since screening.
- Columbia Suicide Severity Rating Scale (C-SSRS) (Baseline version; [Appendix 5](#)).
- 12-lead ECGs (in duplicate) before the first dose on Day 1 at 8 AM.

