## 6.2 Derived Data

- Definition of baseline

With the exception of vital signs measurements, baseline is defined as the last non-missing value prior to the receiving the first dose of study medication. For vital signs measurements, the last screening measurement will be used as baseline.

All tabulations involving change from baseline data will only include subjects with cohort data i.e. with data at baseline and at follow-up. Change from baseline will be calculated as follow-up values minus baseline value.

- Incomplete dates

All incomplete dates will be included in the clinical database as they were entered in the eCRF. Thereafter for calculation purposes, the incomplete dates will be completed using pre-defined rules. If a day or month is not recorded it will be replaced by the first day of the month or January respectively, provided this does not contradict any other dates recorded. For missing adverse events and medications dates/times during the trial, the worst-case date will be used (e.g. the end of the month for a stop date and 23:59 for the stop time, the date/time of initial dose for start of AE i.e. all events with missing start dates will be assumed to be treatment emergent).

- Ambiguous values

In the case where a variable is recorded as “ $>x$ ”, “ $\geq x$ ”, “ $<x$ ” or “ $\leq x$ ”, then for analysis purposes a value of x will be taken. Where a range of values is quoted the midpoint of the range will be taken.

- Questionnaire Data

In the event that component items used to calculate total scores for questionnaire data e.g. SOWS Gossop score are missing then the total scores will also be set to missing.

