### **6.10 Change to Planned Protocol Analysis**

The following changes have been made to the planned protocol analyses sections:

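### SAP 6.2 takes the vital-sign baseline from screening, although a pre-dose Day 1 reading is collected and both documents place Baseline there; the departure is unexplained and not declared in SAP 6.10

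*SAP*

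**What the plan says.** The general rule in SAP 6.2 is: "With the exception of vital signs measurements, baseline is defined as the last non-missing value prior to the receiving the first dose of study medication". Vital signs are the one exception: "For vital signs measurements, the last screening measurement will be used as baseline". No reason is given.

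Protocol 15.2 says "The Baseline period is the morning of admission to the study, before dosing", and adds "The assessments listed below will be performed during the Baseline period before dosing". The list that follows includes resting and standing blood pressure and pulse. Table 1 of the protocol marks vital signs in the Baseline (Day 1) column. The SAP reproduces that table, with the same definition in its note (a).

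The protocol synopsis lists as a safety endpoint: "Descriptive evaluation of vital signs (actual and change from baseline) for each time point". SAP 6.9 (Vital Signs Measurements) tabulates change from baseline for sitting and standing readings. It also defines four PCS criteria, each of which combines an absolute limit with a change from baseline: two for low pressure and two for high.

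SAP 6.10 opens with "The following changes have been made to the planned protocol analyses sections". Its only vital-sign entry concerns the count of missing standing readings.

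**The concern.** This is a single-arm safety study of a drug with antihypertensive action, and change from baseline in blood pressure and pulse is a named safety endpoint. The reference value should be the last one before the drug, unless there is a stated reason to choose another. The screening value has three weaknesses in that role.

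- **It is older.** Protocol 15.1 says "Screening assessments must be completed within a 9-day time period", with a further visit window of plus or minus 2 days. Anything that moves blood pressure between screening and Day 1 is booked as change on treatment.
- **It is selected.** Screening resting values decide eligibility, for example "resting systolic blood pressure less than 95 mmHg or symptomatic hypotension". A subject who first fails and then enters under the 2-of-3 repeat rule must end on a passing value, and that value can be the last screening measurement.
- **It turns the Day 1 pre-dose reading into a follow-up reading.** SAP 6.9 admits every value to the PCS summary. Nothing in the text stops a reading taken before any drug from being counted as a PCS event.

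**Working it through.** The documents state no variance, PCS rate or expected change, so there is no figure of the plan's to reproduce. What follows is an illustration of size.

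**Inputs from the documents**
- Eligibility limits (Protocol 11.2.2): systolic (SBP) 95 to 155, diastolic (DBP) 65 to 95, pulse at least 55; excluded if 2 of 3 readings fail.
- Low-SBP PCS criterion (SAP 6.9): 90 mmHg or lower, with a fall of at least 20 from baseline.
- Enrollment (SAP 2): 250 to 500.

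**Assumptions, not in the documents**
- Mean/SD of SBP with DBP: 115/13 with 72/9, 120/14 with 76/10, 125/15 with 80/10.
- SBP-DBP correlation 0.6; between-visit correlation r of 0.5 or 0.7.
- A shift between screening and Day 1 of -5 to +10 mmHg SBP (0.6 of that for DBP), persisting to follow-up.
- Drug effect 0, or -10 mmHg SBP with -7 DBP.

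**Step 1: sign of the selection effect.** For one screening reading and no drug effect, the expected change is

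shift + (1 - r) x (population mean - mean of readings that pass).

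The limits are two-sided, with midpoints (95 + 155)/2 = 125 for SBP and (65 + 95)/2 = 80 for DBP. Below the midpoint, passing readings average above the population mean and the spurious change is negative. At the midpoint it is about zero, and above it positive. Pulse has only a lower limit, so selection there can act only downward; I have not sized it.

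**Step 2: size, no shift.** The simulation applies the 2-of-3 rule and takes the last screening value as baseline. Mean changes assume no drug effect. PCS columns give the percentage of single follow-up readings meeting the low-SBP criterion with a -10 mmHg drug effect.

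| Mean SBP / DBP | r | Mean change SBP / DBP | PCS, screening baseline | PCS, Day 1 baseline |
|---|---|---|---|---|
| 115 / 72 | 0.5 | -1.8 / -1.8 | 6.8 | 5.4 |
| 115 / 72 | 0.7 | -1.12 / -1.09 | 4.35 | 3.31 |
| 120 / 76 | 0.5 | -1.05 / -1.04 | 4.80 | 4.06 |
| 120 / 76 | 0.7 | -0.63 / -0.62 | 3.19 | 2.54 |
| 125 / 80 | 0.5 | -0.03 / -0.03 | 3.40 | 2.98 |
| 125 / 80 | 0.7 | 0.02 / 0.00 | 2.41 | 1.99 |

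With the Day 1 baseline and no drug effect, mean change is 0.0 in every row. The PCS ratio runs from 3.40/2.98 = 1.14 to 4.35/3.31 = 1.31. The difference runs from 0.4 to 1.4 percentage points, which is 0.004 x 250 = 1 to 0.014 x 500 = 7 subjects per reading.

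**Step 3: higher means.** A variant with between-subject SD 12 (SBP) and 8 (DBP), and within-subject SD 6 to 10 and 6 to 8, gives +0.2 to +0.5 mmHg at mean SBP 130 and +0.7 to +1.1 at mean DBP 84.

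**Step 4: drift.** A shift of -5 to +10 mmHg gives a spurious SBP change of -6.8 to +10.0 mmHg. With the -10 mmHg drug effect, low-SBP PCS is 5.8 to 14.4% (screening baseline) against 3.7 to 9.0% (Day 1) for a shift of -5. For a shift of +10 it is 0.2 to 1.0% against 0.4 to 1.3%, so the direction reverses.

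**Step 5: pre-dose PCS events.** In this model the pre-dose Day 1 reading behaves like an undrugged follow-up reading. With no shift and mean SBP 120 or 125, 0.24 to 0.72% of such readings meet the low-SBP criterion against the screening baseline: 0.0024 x 250 = 0.6 to 0.0072 x 500 = 3.6 subjects.

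**The case against.** The case for the plan has real substance.

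- **The screen value is the protocol's own reference elsewhere.** It serves the resting dose-hold criteria (13.2.2), the matching adverse-event labels (10.4) and the relative QTcF rule (13.2.3). Using it throughout keeps one reference. This is plausible, but the SAP does not say it. Those rules name the screen value, while the endpoint and the PCS criteria say baseline.
- **The protocol is not uniform.** Section 17 never names the reference for vital-sign change, and 15.5.3 calls screening ECGs baseline. So this is an undeclared choice against the documents' Baseline definition, not the breach of an explicit analysis rule.
- **Other baselines also come from screening.** A reader might infer that every other variable uses Day 1. Laboratory tests and weight normally use screening values, because no later pre-dose value is scheduled. For vital signs a later value is scheduled and is passed over.
- **Opioid status.** A reader might infer that screening and Day 1 are separated by days of changing opioid dose. The documents do not establish that. The synopsis puts the opioid change on Day 1 itself; only 10.1 and 13.2.1 also allow a start at emergence of symptoms, so that the change could come first. Under that alternative, Day 1 may already reflect early withdrawal. If such a shift faded after Day 1, the Day 1 baseline would carry the error; the calculation above assumes that it persists.
- **Reach.** Adverse events of special interest, dose-hold counts and the absolute blood pressure and pulse discontinuation limits do not use this baseline. Observed values are tabulated beside the changes, and the PCS criteria also require an absolute limit.
- **Pre-dose PCS events.** The statement that all values are included may have been meant only to admit repeats and unscheduled readings. The text does not say so.

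**Conclusion.** The point stands as a moderate one that should be corrected. The SAP passes over a scheduled pre-dose reading that fits the Baseline definition in both documents, without giving a reason or declaring it. It affects the change-from-baseline tables and all four PCS criteria.

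The eligibility effect on mean blood pressure is small: about 0 to -2 mmHg under the main assumptions, and near zero or positive if the population mean is higher. The larger exposure is drift before Day 1, whose size and sign the documents do not give. It would therefore be wrong to conclude that the screening baseline generally overstates hypotension, or that every hypotension result in the study is affected. It would also be wrong to expect a Day 1 baseline to isolate the drug effect. It removes selection and pre-dose drift, but in a single-arm study withdrawal continues to evolve after Day 1 under either baseline.

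**What to change.** 1. In SAP 6.2, define the vital-sign baseline for change and PCS tables as the last pre-dose Day 1 reading, with the last screening value as fallback if it is missing.
2. In SAP 6.9, count only readings after the first dose as PCS events.
3. Keep the screen value for dose-hold tables and any other rule that names it.
4. Show change from screening as a sensitivity table.
5. Record the baseline choice and its reason in SAP 6.10. If screening is kept on purpose, make the Day 1 version the sensitivity table, and still apply item 2.
6. Reconcile the protocol synopsis with 10.1 and 13.2.1 on when lofexidine starts relative to the opioid change, so that a reader knows what the Day 1 reading represents.

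The cost is a few sentences and one extra table; no new data are needed. The drawbacks are two reference values that must be labelled clearly, and a Day 1 baseline that may reflect early withdrawal in some subjects.

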## 6.3 Analysis populations

The Enrolled Population includes all subjects screened into the study irrespective of whether they received the study medication.

The Safety Population includes all subjects who received at least one dose of study medication.

With the exception of the disposition table all outputs will use the Safety Population.

## 6.4 Protocol Deviations

A listing of protocol deviations will be provided within [Appendix 16.2](#).

## 6.5 Data Summaries

The data will be summarized in tabular form by treatment (Lofexidine).

Graphical presentations of the data will also be provided where appropriate.

## 6.6 Disposition of Subjects

The following will be summarized:

- The number of subjects who are included in the Enrolled Population,
- The number of enrolled subjects that enrolled but failed to be dosed along with the reasons,
- The number of subjects that completed the inpatient treatment period and the number of subjects who transitioned to outpatient at Day 4, 5, 6 and 7 (each day will be displayed separately).
- The number of enrolled subjects that completed the study (took one dose on Day 7). Additionally, the reason for withdrawal will be summarized as follows:
  - Lack of effectiveness
  - AE related to study drug
  - Withdrew consent
  - Lost to Follow-Up
  - AE unrelated to the study drug or withdrawal symptoms (e.g. concomitant illness)
  - There is evidence of contraband drug use while participating in the study
  - Requires treatment with an exclusionary drug
  - Lack of compliance with protocol and/or unit procedures
  - Other, specify

## 6.7 Baseline Comparability

### 6.7.1 Study Population

Subject demographics and baseline characteristics will be presented for all subjects within the Safety Population.

Co-administration categories will include the following:

- Any co-administration of Buprenorphine
- Any co-administration of Methadone
- Other (no co-administration of buprenorphine or methadone)

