## **17.2 Assessment of Effectiveness**

Effectiveness measures will be summarized for the following subject cohorts:

- All exposed subjects;
- Subjects undergoing abrupt and total withdrawal;
- Subjects undergoing buprenorphine-assisted withdrawal;
- Subjects transitioning to naltrexone maintenance;
- Subjects transitioning to buprenorphine maintenance;
- Subjects undergoing partial withdrawal to lower dose (e.g., chronic opioid medication for pain); and
- Any other identifiable cohorts not otherwise noted.

Descriptive statistics will be provided for:

- Demographics and baseline characteristics;
- SOWS-Gossop;
- COWS numerical score;
- COWS severity category (i.e., mild, moderate, moderately severe, severe);
- Number/proportion of subjects successfully completing their pre-defined withdrawal treatment goal (e.g., planned detoxification/transition) as assessed by the Principal Investigator;
- Distribution of number of days required to complete withdrawal treatment goal by category;
- Concomitant medications; and
- Evaluation of subject treatment status 30 days after last dose.

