### **17.3 Assessment of Safety**

Safety summaries will be provided for subjects who received lofexidine; any safety information on subjects who provide informed consent but do not receive lofexidine will be included in listings.

Safety measures will be summarized for the following subject cohorts:

- All exposed subjects;
- Subjects undergoing abrupt and total withdrawal;
- Subjects undergoing buprenorphine-assisted withdrawal;
- Subjects transitioning to naltrexone maintenance;
- Subjects transitioning to buprenorphine maintenance;
- Subjects undergoing partial withdrawal to lower dose (e.g., chronic opioid medication for pain); and
- Any other identifiable cohorts not otherwise noted.

Descriptive statistics will be provided for:

- AEs;
- AEs of special interest, including orthostatic hypotension, orthostatic bradycardia, and syncope;
- Vital signs;
- ECGs;
- Clinical laboratory tests; and
- C-SSRS.

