### 6.8 Effectiveness Endpoints

#### *Treatment Goal*

Number and proportion of subjects' baseline treatment goal will be presented overall and for each co-administration category.

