#### *Status of Pre-defined Withdrawal Treatment Goal as Assessed by the Site Investigator*

Number and proportion of subjects successfully completing their pre-defined withdrawal treatment goal as assessed by the Site Investigator at Day 7 or early termination (last assessment) and Day 14 will be presented overall and for each co-administration category. The number and proportion of subjects who relapsed during the study will be presented overall by study day.

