#### *Questionnaires*

Summary statistics will be provided overall and for each co-administration category by study day for Days 1-14:

- SOWS-Gossop

- COWS

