#### *Concomitant Medications*

For each of Days 1 to 14, each subject's number of concomitant medication taken will be treated as a continuous variable. Descriptive statistics will be provided on the as-observed data on each study day and also overall study days.

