#### *Details of the Day 30 Follow-Up*

- Lost to Follow-up
- Whether subject entered one of the following programs:
  - None
  - Methadone
  - Buprenorphine
  - Naltrexone
  - Other
- Whether subject relapsed to drug use after exiting the study (Yes, No)

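### SAP 6.8 and 6.9 specify no outcome for any of the five withdrawal-scenario cohorts in protocol 17.2 and 17.3, and SAP 6.10 does not declare the change

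*SAP*

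**What the plan says.** On effectiveness, protocol 17.2 states: "Effectiveness measures will be summarized for the following subject cohorts". Protocol 17.3 does the same for safety: "Safety measures will be summarized for the following subject cohorts". Both list all exposed subjects, the same five withdrawal scenarios, and a residual entry for other cohorts that can be identified. Protocol 17.1 leaves the detailed methods to the SAP.

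SAP 6.7.1 sets up a different grouping: "Any co-administration of Buprenorphine", the equivalent for methadone, and an Other group with neither drug. This grouping carries most of what follows.

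- Treatment goal (SAP 6.8): "baseline treatment goal will be presented overall and for each co-administration category".
- Goal completion (SAP 6.8): results "at Day 7 or early termination (last assessment) and Day 14 will be presented overall and for each co-administration category".
- SOWS-Gossop and COWS (SAP 6.8): "Summary statistics will be provided overall and for each co-administration category by study day for Days 1-14".
- Concomitant medication counts (SAP 6.8): "Descriptive statistics will be provided on the as-observed data on each study day and also overall study days", with no subgroup stated.
- Day 30 follow-up (SAP 6.8): a list of items, with no subgroup stated.
- Safety (SAP 6.9): the Safety Population, the three co-administration categories, and any further co-administration categories that can be identified. Adverse events are also split by inpatient and outpatient phase.

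SAP 6.10 declares three changes from the protocol: an added methadone-assisted cohort, adverse event summaries by phase, and a count of missing standing vital signs.

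**The concern.** The primary objective, repeated in SAP section 1, is safety at the studied doses across varied clinical scenarios. The protocol turns that into named cohorts. The SAP is where they should become specified tables, and its text does not do this.

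If the SAP is followed as written, the report can say how many subjects had each treatment goal. It cannot say how adverse events, blood pressure, withdrawal scores or goal completion looked within a scenario. SAP 6.1 allows extra tables when the data warrant them, but scenario tables added by that route would be chosen after open-label results had been seen. A reader who relied on SAP 6.10 to learn what had changed would not know that the protocol cohorts are missing from the body of the SAP.

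**Working it through.** The plan gives no figure to reproduce here. The check is a comparison of the two texts, with one short calculation on cohort size.

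**Step 1. Breakdown required against breakdown specified.**

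| Measure | Protocol | SAP text |
|---|---|---|
| Goal completion | Scenario cohorts (17.2) | Overall; co-administration category |
| SOWS-Gossop, COWS | Scenario cohorts (17.2) | Overall; co-administration category; by day |
| Concomitant medications | Scenario cohorts (17.2) | By day and over all days (6.8); coded terms overall (6.9) |
| Status 30 days after last dose | Scenario cohorts (17.2) | No subgroup stated |
| Adverse events | Scenario cohorts (17.3) | Overall; phase; co-administration category |
| Vital signs | Scenario cohorts (17.3) | Overall; co-administration category; by day |
| Laboratory tests, C-SSRS | Scenario cohorts (17.3) | Covered by the general category list opening 6.9; C-SSRS also by phase |
| ECG | Scenario cohorts (17.3) | Deferred to a separate SAP, not available here |

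Named scenario cohorts in the protocol: 5. Cohorts for which SAP 6.8 or 6.9 specifies an outcome: 0.

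**Step 2. Can the SAP categories stand in for the cohorts?** No. Buprenorphine-assisted withdrawal, transition to buprenorphine and a buprenorphine taper can all fall in the buprenorphine category. Abrupt withdrawal, transition to naltrexone and reduction of a pain opioid can all fall in Other when neither agonist is given. Crossing treatment goal with co-administration category gives the number of subjects in each cell, without their outcomes. The residual entry in 6.9 covers safety only and is confined to co-administration. It might isolate naltrexone, but it would not separate abrupt withdrawal from pain-opioid reduction when neither subject takes an agonist.

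**Step 3. Is the change declared?** None of the 3 changes in SAP 6.10 says that the scenario cohorts were replaced. The one cohort change is an addition, and that methadone-assisted cohort does not appear in 6.8 or 6.9, which list only co-administered methadone.

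**Step 4. Can the cohorts be derived?** Protocol 15.1 records four goals at screening: abrupt total withdrawal, agonist-assisted total withdrawal, dose reduction, and transition. Two assignments need a rule. Planned naltrexone is recorded within both the abrupt and the agonist-assisted goals. There is one agonist-assisted goal, so buprenorphine-assisted and methadone-assisted subjects must be told apart by another item. Appendix 4 may record the drug, but it is not in the copy available.

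**Step 5. How much could a small cohort show?** With no events in n subjects, the exact two-sided 95% upper limit is 1 − 0.025^(1/n). For n = 20 this is 1 − 0.025^(1/20) = 16.8%. For n = 50 it is 1 − 0.025^(1/50) = 7.1%. These cohort sizes are illustrative, as the documents do not forecast the scenario mix.

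**The case against.** The co-administration grouping has a sound basis. Amendment 1 wanted evidence on giving lofexidine with methadone or buprenorphine, and the only scenario enrolment targets are 50 subjects for each of those two drugs. Everything is descriptive and single-arm, so no error rate or sample size is affected. The protocol cohorts overlap and need a mapping of their own. All of this stands. It supports keeping the co-administration tables, but it does not remove the protocol's instruction to summarize by scenario.

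Three stronger readings are tempting, and the documents do not support them.

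- *The sponsor abandoned the scenario cohorts.* SAP section 1 bases the analysis on the protocol, and 6.10 speaks of adding a cohort, which presupposes that the others remain. The SAP table list shows only column headers in this copy, and some later pages were removed. Incomplete drafting is as plausible as abandonment.
- *The co-administration categories are too undefined to apply.* The word Any naturally covers an agonist first taken as needed after Day 1, and places a subject who takes both drugs in both groups. SAP 6.7.2 treats medications that ended before the first lofexidine dose as prior, 6.9 codes concomitant medications from that dose onward, and protocol 15.6.2 names the eCRF. Together these give an ordinary start boundary and data source. One loose end remains: SAP 6.7.2 takes the primary opioid of abuse from the concomitant medication eCRF, so it is worth stating whether the opioid being withdrawn counts.
- *Pooling hides a known amount of risk.* The documents give neither scenario shares nor event rates, so the size and direction of any masking cannot be estimated.

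**Conclusion.** The point holds as a mismatch between protocol 17.2 and 17.3 and the text of SAP 6.8 to 6.10. Outcomes are specified for 0 of 5 protocol cohorts, and 0 of 3 declared changes disclose it. It should be fixed because scenario is the axis named in the primary objective. It does not undermine the overall Safety Population summaries. The conclusion rests on the visible SAP text and would soften if the final table list contains tables by scenario cohort. Even then 6.8, 6.9 and 6.10 would need to be brought into line.

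**What to change.** 1. In SAP 6.8 and 6.9, add the main effectiveness and safety summaries by the protocol 17.2 and 17.3 cohorts plus methadone-assisted withdrawal. Derive the cohorts from the treatment goal recorded at screening, with a written mapping that says how naltrexone goals are assigned and how buprenorphine-assisted and methadone-assisted withdrawal are told apart. Keep the co-administration tables.
2. Correct SAP 6.10 to declare the co-administration grouping and state how it relates to the protocol cohorts.
3. As a minor clarification in SAP 6.7.1, state that the two agonist categories may overlap, that co-administration means use after the first lofexidine dose, and whether the opioid being withdrawn counts.

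The cost is SAP wording and programming, since the treatment goal and dated concomitant medications are already collected. The drawback is more tables, some with few subjects. These should be labelled descriptive: a cohort of 20 with no events is still compatible with a rate of up to 16.8%.
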